6.7 Management of IP related toxicities

If a patient experiences a CTCAE grade 3 or higher and/or unacceptable toxicity (any grade) not attributable to the disease or disease-related processes under investigation, where the Investigator considers the AE of concern to be specifically associated with AZD9291, dosing will be interrupted and supportive therapy administered as required in accordance with local practice/guidelines.

If the toxicity resolves or reverts to \leq CTCAE grade 2 within 3 weeks of onset, treatment with AZD9291 may be restarted at the same dose (80 mg) or a lower dose (40 mg) using the rules below for dose modifications (Table 9) and with discussion and agreement with the AstraZeneca Study Team Physician as needed. There will be no individual modifications to dosing schedule in response to toxicity, only potential dose reduction or dose interruption.

If the toxicity does not resolve to \leq CTCAE grade 2 after 3 weeks, then the patient should be withdrawn from the study and observed until resolution of the toxicity.

Table 9 Dose interventions

Intervention	AZD9291 Dose
Starting Dose	80 mg

Table 9 **Dose interventions**

Intervention	AZD9291 Dose
Reduced Dose –1	40 mg

On resolution of toxicity within 3 weeks:

- If an AE subsequently requires dose interruption, AZD9291 may restart at the same dose or the reduced dose, on resolution/improvement of the AE at the discretion of the Investigator.

If new or worsening pulmonary symptoms (eg, dyspnoea) or radiological abnormality suggestive of interstitial lung disease is observed, an interruption in study treatment dosing is recommended, and the AstraZeneca study team should be informed. A questionnaire regarding the results of the full diagnostic workup (including high-resolution computed tomography (HRCT), blood and sputum culture, haematological parameters) will be sent to Investigators. It is strongly recommended to perform a full diagnostic workup, to exclude alternative causes such as lymphangitic carcinomatosis, infection, allergy, cardiogenic edema, or pulmonary hemorrhage. In the presence of confirmatory HRCT scans where other causes of respiratory symptoms have been excluded, a diagnosis of interstitial lung disease should be considered and study treatment permanently discontinued.

In the absence of a diagnosis of interstitial lung disease study treatment may be restarted following consultation with the AstraZeneca Study Team Physician.

Patients with QTcF prolongation fulfilling the following criteria (i.e. confirmed QTcF prolongation to > 500 msec absolute or a > 60 msec increase from baseline) should have study treatment interrupted and regular ECGs performed until resolution to baseline. If the toxicity does not resolve to ≤ grade 1 within 3 weeks the patient will be permanently withdrawn from study treatment.

Patients experiencing corneal ulceration or Interstitial Lung Disease (ILD) will not be permitted to restart study treatment.

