3.7 Withdrawal from the study

The term withdrawal from the study refers to both discontinuation from study treatment and study assessments.

Patients may be withdrawn from the study for the following reasons:

- Screen failure
- Death
- Withdrawal of consent

If a patient wishes to withdraw their consent to both treatment and study assessments, they should be asked if they are willing to continue with survival follow-up (which can be conducted by telephone – see [Section 4.3.4](#)). If a patient wishes to withdraw their consent to further participation in the study entirely, including survival follow-up this should be clearly documented in the patient notes and in the clinical study database.

Withdrawn patients will not be replaced.

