3.6.1 Procedures for discontinuation of a subject from investigational product

Previous text:

Any subject who discontinues study treatment for reasons other than objective disease progression should have tumour assessments performed as scheduled in the protocol (See Table 1) until objective disease progression is documented or death occurs, unless consent is withdrawn. Study procedures related to PROs, SAEs and anti-cancer treatment must be captured until the subject no longer has RECIST 1.1 assessments (disease progression or permanent withdrawal from the study).

Revised text:

Any subject who discontinues study treatment for reasons other than objective disease progression should have tumour assessments performed as scheduled in the protocol (See Table 1) until objective disease progression is documented or death occurs, unless consent is withdrawn. ~~Study procedures related to PROs, SAEs and anti-cancer treatment must be captured until the subject no longer has RECIST 1.1 assessments (disease progression or permanent withdrawal from the study).~~ **Refer to Section 4.3 for further details.**

Section of protocol affected:

Table 1 Study Plan

Previous text:

Footnote r Following AZD9291 discontinuation, SAEs considered related to study procedures should continue to be collected until disease progression.

Revised text:

Footnote r Following AZD9291 discontinuation, SAEs considered related to study procedures should continue to be collected **as outlined in Table 8.**

Time relative to dose	Screening (baseline)	Cycle 1 Day 1	Cycle 2 Day 1	Cycle 3 Day 1
24 hours (±1 hour)	X			X (D2, pre-dose)

1 Since there is no dosing at Screening, ECG recordings should start at a time that would be consistent with planned dosing times at Cycle 1 Day 1, Cycle 2 Day 1 and Cycle 3 Day 1 (for baseline purposes).

Revised text:

Time relative to dose	Screening (baseline)	Cycle 1 Day 1	Cycle 2 Day 1	Cycle 3 Day 1
Pre-dose (-10 to 0 min) ²	X ¹	X	X	X
1 hour (±5 min)	X	X		X
2 hours (±10 min)	X	X		X
4 hours (±10 min)	X	X		X
6 hours (±10 min)	X	X		X
8 hours (±10 min)	X	X		X
10 hours (±10 min)	X			X
12 hours (±1 hour)	X			X
24 hours (±1 hour)	X			X (D2, pre-dose)

1 Since there is no dosing at Screening, ECG recordings should start at a time that would be consistent with planned dosing times at Cycle 1 Day 1, Cycle 2 Day 1 and Cycle 3 Day 1 (for baseline purposes).

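### Section 6.7 withdraws patients with persistent drug-related toxicity from the study rather than from treatment, which contradicts Sections 3.6, 3.6.1, 3.7 and 4.3.3 and, taken literally, ends their scans

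*Supplement*

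**What the plan says.** Section 6.7 opens with a general rule for grade 3 or higher, or unacceptable, toxicity: "where the Investigator considers the AE of concern to be specifically associated with AZD9291, dosing will be interrupted". Recovery allows a restart: "CTCAE grade 2 within 3 weeks of onset, treatment with AZD9291 may be restarted", at 80 mg or 40 mg. If the toxicity is still above grade 2 after 3 weeks, "then the patient should be withdrawn from the study and observed until resolution of the toxicity".

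Section 3.7 gives that expression a fixed meaning: "The term withdrawal from the study refers to both discontinuation from study treatment and study assessments". It lists three reasons for it: screen failure, death and withdrawal of consent. Toxicity is not among them.

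Section 3.6 lists an adverse event as a reason to discontinue the investigational product. For such a patient, Section 3.6.1 as revised by Amendment 2 says: "Any subject who discontinues study treatment for reasons other than objective disease progression should have tumour assessments performed as scheduled in the protocol", until progression or death unless consent is withdrawn. Section 4.3.3 and note (b) to Figure 1 say the same in substance.

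The QTcF paragraph later in Section 6.7 ends treatment only: "If the toxicity does not resolve to ≤ grade 1 within 3 weeks the patient will be permanently withdrawn from study treatment".

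The amendments leave both the general rule and the QTcF paragraph as they were. Amendment 2 touches only Section 6.7.2.

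**The concern.** The general rule uses a defined term for something the rest of the protocol handles differently. A site that follows Section 6.7 to the letter closes the patient's study participation, and the 6-weekly scans stop. A site that follows Sections 3.6 and 3.6.1 stops the drug and keeps scanning. Two patients with the same toxicity could be followed differently.

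The scans at stake feed the primary endpoint and two secondary ones:

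- **ORR** needs a response confirmed at least 4 weeks later (Section 8.4). A responder who leaves before the next scan is not confirmed.
- **PFS** is censored at the last evaluable assessment, or at 0 days if there is none and no death within two visits of baseline. A death after three or more missed assessments is censored too.
- **DoR** takes its end date, or its censoring time, from PFS.

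The loss would be tied to toxicity and so not random. OS is better protected, because Section 4.3.4 asks sites to establish the vital status of withdrawn patients as well.

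**Working it through.** The plan states no figure on this point to reproduce. The check compares the texts and then bounds the effect.

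**1. The texts side by side, for a patient still above grade 2 at 3 weeks**

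| Place | Patient leaves | Scans afterwards |
|---|---|---|
| 6.7, general rule, read with 3.7 | study (treatment and assessments) | stop |
| 3.7, list of reasons | toxicity not a listed reason | – |
| 3.6, 3.6.1, 4.3.3, Figure 1 note (b) | product only | continue to progression |
| 6.7, QTcF paragraph | study treatment only | continue under 3.6.1 |

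Only the general rule ends assessments for toxicity.

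**2. When an exit would cost a confirmed response**

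Scans fall every 6 weeks from first dose (Table 1): week 6 is Day 1 + 42 = 43, week 12 is Day 1 + 84 = 85, and week 18 is Day 1 + 126 = 127. Exit day = onset day + 21.

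- Onset Days 1 to 21, exit Days 22 to 42: no scheduled on-study scan.
- Onset Days 22 to 63, exit Days 43 to 84: at most the week-6 scan, so a week-6 response cannot be confirmed.
- Onset Days 64 to 105, exit Days 85 to 126: a week-6 response can be confirmed, but one first seen at week 12 cannot.
- Onset from Day 106: mainly DoR and PFS follow-up are cut.

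The ±7-day window moves these limits by up to a week.

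**3. Size for ORR**

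The evaluable-for-response set (Section 8.3.2) requires one dose and measurable disease at baseline by central review. A patient who leaves early stays in the denominator and counts as a non-responder, so the effect on ORR is downward.

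- Maximum per patient: 1/175 = 0.57 points overall; 1/125 = 0.8 and 1/50 = 2.0 points in the two cohorts. These use the planned numbers; a smaller evaluable set would raise them slightly.
- Expected per patient overall: 0.571 × 0.40 = 0.23 points at the ORR used as the example in Section 8.2, and 0.571 × 0.50 = 0.29 at the phase I rate in Section 1.3.

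The documents do not say how many such patients to expect. Over an assumed range:

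| Patients (assumed) | Maximum loss | Expected, ORR 40% to 50% |
|---|---|---|
| 1 | 0.6 points | 0.2 to 0.3 |
| 3 | 1.7 points | 0.7 to 0.9 |
| 5 | 2.9 points | 1.1 to 1.4 |

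The stated precision for the whole study is ±8 points. The expected figures assume that these patients would have responded as often as the others, and that each loses the confirmation.

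**The case against.** The best defence is that the intent is plain elsewhere. Section 3.6 puts adverse events under product discontinuation, Section 3.7 leaves toxicity out, and three other places require scans to continue. The general rule itself keeps the patient under observation until the toxicity resolves. Most sites would probably go on scanning. This stands, and it is why the point is small. It does not remove the contradiction: Section 6.7 is where an investigator managing toxicity will look, and observing a toxicity is not a tumour assessment.

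A reader might infer something stronger: that Section 6.7 leaves open which rule governs a QTcF interruption, since the general rule allows a restart at grade 2 while the QTcF paragraph withdraws the patient at 3 weeks. The documents do not support this. The QTcF paragraph is written for patients meeting stated QTcF criteria and is mandatory, whereas the general rule only permits a restart, so a site can comply with both. The ban on restarting after ILD or corneal ulceration is likewise a stricter specific rule following a general one. The line on later interruptions ("AZD9291 may restart at the same dose or the reduced dose, on resolution/improvement of the AE at the discretion of the Investigator") concerns adverse events in general and does not displace the QTcF paragraph.

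That paragraph states no restart dose. However, its instruction that patients "should have study treatment interrupted and regular ECGs performed until resolution to baseline" can be read as requiring return to baseline before restart. Adding a sentence that allows restart at grade 1 could therefore loosen a cardiac safety rule, and none is proposed.

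**Conclusion.** The contradiction is real but minor. On its wording, the general rule in Section 6.7 ends study assessments for persistent AZD9291-related toxicity, against Sections 3.6, 3.6.1, 3.7 and 4.3.3 and the Figure 1 note. Harm arises only where a site follows it literally. The cost is then at most 0.57 points of overall ORR per patient, plus shortened DoR and PFS follow-up that is linked to toxicity.

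That few patients would remain above grade 2 after 3 weeks off drug is an assumption; the documents give no count. On that assumption the ORR conclusion would not change, and any error in ORR would understate the response rate. The direction of any effect on DoR and PFS cannot be settled from the documents. The sample size and stated precision are unaffected, and the QTcF paragraph needs no change for this reason.

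**What to change.** In the general rule of Section 6.7, replace *withdrawn from the study* with *permanently withdrawn from study treatment*, and add that follow-up continues under Sections 3.6.1 and 4.3. Keep the observation until the toxicity resolves.

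The cross-reference matters because Appendix D, Section 4.1 describes scans as running until study treatment is discontinued, which also departs from Section 3.6.1.

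The cost is one phrase and one cross-reference. It adds no visit or scan beyond those Sections 3.6.1 and 4.3.3 already require, and it leaves dosing rules, sample size and analysis unchanged.

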6.7.1 Skin reactions

Recommendations for appropriate management of skin reactions, including guidance on dose-adjustments for clinically significant and/or intolerable skin reactions that are considered by the investigator to be causally related to AZD9291 will be provided to investigators.

Skin reactions are to be reported as AEs in the CRF, with additional details captured in the "SKNREAC" CRF:

- Changes in the characteristics of skin reactions will be collected in the "SKNREAC" CRF.
- Changes in the CTCAE grade of skin reactions will be collected in the AE CRF.

Photographs of skin reactions may be collected and these photographs should be available for central review by AstraZeneca and for external expert dermatological review if required.

Skin biopsies may be taken of skin reactions.

6.7.2 Diarrhoea

Recommendations for appropriate management of diarrhoea, including dose-adjustments for adverse events of diarrhoea that are of CTCAE grade ≥ 3 or that are clinically significant and/or intolerable and considered by the investigator to be causally related to AZD9291, will be provided to investigators.

6.8 Study governance and oversight

6.8.1 Steering Committee

A Steering Committee comprising of the principal investigators for study D5160C00002, in addition to principal investigators from the other AZD9291 pivotal studies will provide advice on any aspect of the study design or conduct based on requests from the sponsor and assure consistency across the entire AZD9291 pivotal programme.

No Data Monitoring Committee (DMC) is planned, as this study is an open-label non-randomised phase II study. In addition the safety profile of AZD9291 from the ongoing phase I trial in a similar NSCLC patient population is modest, predictable with no reported life-threatening adverse events. There is therefore no requirement for pre-planned specified expert independent safety reviews in this study.

7. INVESTIGATIONAL PRODUCT AND OTHER TREATMENTS

7.1 Identity of investigational product(s)

Investigational product	Dosage form and strength	Manufacturer
AZD9291	40-80 mg Tablets	AstraZeneca

7.2 Dose and treatment regimens

AstraZeneca will supply AZD9291 as tablets for oral administration as a single daily dose of 80 mg. Patients (with the exception of patients with insulin dependent diabetes) must fast for ≥ 1 hours prior to taking a dose to ≥ 2 hour post dose. Water is permitted during this fasting period. Patients will be required to fast (water only) for at least 8 hours prior to the collection of a fasting glucose sample as per the study plan (Table 1) and Section 5.2.1.

At each dispensing visit, sufficient AZD9291 for 21 days treatment, plus overage, will be dispensed. Individual bottles will be dispensed in accordance with the medication identification numbers provided by the IVRS/IWRS.

Patients should swallow one AZD9291 80 mg tablets once daily, commencing on Cycle 1 Day 1. Tablets should be taken whole with water.

The initial dose of AZD9291 can be reduced under circumstances described in Section 6.7.

On clinic days on which PK samples are scheduled to be taken, the dosing should be delayed until arrival at the clinic and until the pre-dose ECG has been performed followed by the pre-dose PK sample. Patients should not take their dose until instructed to do so by site personnel.

Doses should be taken approximately 24 hours apart at the same timepoint each day. On PK and ctDNA sampling days, the doses should be delayed until instructed to take by site personnel. Doses should not be missed. If a patient misses taking a scheduled dose, within a window of 12 hours, it is acceptable to take the dose. If it is more than 12 hours after the dose time, the missed dose should not be taken, and patients should be instructed to take the next dose at the next scheduled time. If a patient vomits after taking their AZD9291, they should not make up for this dose, but should take the next scheduled dose.

Any change from dosing schedule, dose interruptions, dose reductions should be recorded in the eCRF.

Tablets will be packed in high-density polyethylene (HDPE) bottles with child-resistant closures. Bottles will be dispensed to subjects in the AstraZeneca packing provided. The packaging includes bottles, caps and a label. Bottle tamperers should not be broken prior to dispensing study drug to a patient.

Additional information about the Investigational product may be found in the Investigators' Brochure.

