3.3 Subject enrolment

Investigator(s) should keep a record, the subject screening log, of subjects who entered pre-study screening.

The Investigator(s) will:

1. Obtain signed informed consent from the potential subject before any study specific procedures are performed.
2. Assign potential subject a unique 7-digit enrolment number obtained through the IVRS/IWRS in the following format ECCNNXXX: CC being the country code, NN being the centre number and XXX being the patient enrolment code at the centre.
3. Determine subject eligibility. See Section 3.

At Visit 2, once the patient is confirmed to be eligible, the PI or suitably trained delegate will:

4. Perform a drug dispensing call in IVRS/IWRS.

If a subject withdraws from participation in the study, then his/her enrolment code cannot be reused.

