4. STUDY PLAN AND TIMING OF PROCEDURES

Table 1 Study Plan

Visit	Screening	Treatment Period (further treatment cycles as per Cycle 7)								Follow-up Period			For details see Protocol Section
	1	2	3	4	5	6	7-9	10+	Treatment Discontinuation	28-day follow-up	Progression follow-up	Survival follow-up	
Cycle ^a / Day		C1 D1	C1 D8	C1 D15	C2 D1	C3 D1	C4-6 D1	C7 ^b + D1	NA	NA	NA	NA	
Day	-28	1	8	15	22	43	64-106	127+	NA	NA	NA	NA	
Window (days)	NA	0	±2	±2	±7	±7	±7	±7	NA	±7	±7	±7	SECTION:
Informed consent ^c	X												3.3 & 4.1
Submit mandatory tumour tissue sample for mutation analysis ^d	X												4.1 & 5.6
Submit tumour tissue for diagnostic development (optional) ^e	X												4.1, 5.6 & 5.6.3.2
Optional tumour biopsy for exploratory research									X				5.6
Archival tumour tissue ^f	X												5.6
Demography & baseline characteristics	X												4.1
Medical/surgical history	X												4.1
Inclusion/exclusion criteria	X												3
Physical examination, including weight	X	X ^g			X	X	X	X	X				5.2.3 & 5.2.6.2

Table 1 Study Plan

Visit	Screening	Treatment Period (further treatment cycles as per Cycle 7)								Follow-up Period			For details see Protocol Section
	1	2	3	4	5	6	7-9	10+	Treatment Discontinuation	28-day follow-up	Progression follow-up	Survival follow-up	
Cycle ^a / Day		C1 D1	C1 D8	C1 D15	C2 D1	C3 D1	C4-6 D1	C7 ^b + D1	NA	NA	NA	NA	
Day	-28	1	8	15	22	43	64-106	127+	NA	NA	NA	NA	
Window (days)	NA	0	±2	±2	±7	±7	±7	±7	NA	±7	±7	±7	SECTION:
Height	X												5.2.6.2
WHO Performance status	X	X			X	X	X	X	X				4.1
Pregnancy test (pre-menaopausal females only)	X												5.2.1
Ophthalmologic assessment	X	← as clinically indicated →											5.2.7.1
Vital signs ^g	X	X	X	X	X	X	X	X	X				5.2.6
Clinical chemistry/ Haematology/Urinalysis ^g	X ^h	X	X	X	X	X	X	X	X				5.2.1
Digital ECG	X	X	X ^g	X ^g	X ^g	X	X	X	X				5.2.4
Echocardiogram/MUGA	X		← every 12 weeks relative to first dose →										5.2.5
PK blood sample (including metabolites)		X			X	X							5.4
Plasma sample for ctDNA ^g	X ⁱ	X	X	X	X	X	X	← every 6 weeks in line with RECIST assessments ^j →					4.3.3 & 5.6.2
Optional genetic consent and sample	X ^k												5.5

Table 1 Study Plan

Visit	Screening	Treatment Period (further treatment cycles as per Cycle 7)								Follow-up Period			For details see Protocol Section
	1	2	3	4	5	6	7-9	10+	Treatment Discontinuation	28-day follow-up	Progression follow-up	Survival follow-up	

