Cycle ^a / Day		C1 D1	C1 D8	C1 D15	C2 D1	C3 D1	C4-6 D1	C7 ^b + D1	NA	NA	NA	NA	
Day	-28	1	8	15	22	43	64-106	127+	NA	NA	NA	NA	
Window (days)	NA	0	±2	±2	±7	±7	±7	±7	NA	±7	±7	±7	
Optional CSF sample					X (once only) ¹								SECTION: 5.5.2
Tumour assessments (RECIST v1.1) ^m	X	← every 6 weeks relative to first dose until disease progression →										4.2 & 5.1.1	
EORTC QLQ-C30 and EQ-5D-5L (by electronic device)		X ^g	← every 6 weeks relative to first dose →					X		X ⁿ	X ⁿ	5.3.2.1 & 5.3.2.2	
EORTC QLQ LC13 (by electronic device)		X ^g	← weekly relative to first dose →		← every 3 weeks relative to first dose →			X		X ^o	X ^o	5.3.2.1	
PRO-CTCAE (by electronic device) ^p		X ^g	← weekly for first 18 weeks of treatment →				X ^q	X		X ^o	X ^o	5.3.2.3	
Healthcare Resource Use		← →										5.3.2.5	
Dispense study medication		X			X	X	X	X					3.3 & 7.2
Dose with AZD9291		← Daily dosing →											7.2
Concomitant medication & procedures		← →										7.7	
Adverse events		← →										X ^r	6.3 & 6.4

Table 1 Study Plan

Visit	Screening	Treatment Period (further treatment cycles as per Cycle 7)								Follow-up Period			For details see Protocol Section
	1	2	3	4	5	6	7-9	10+	Treatment Discontinuation	28-day follow-up	Progression follow-up	Survival follow-up	
Cycle ^a / Day		C1 D1	C1 D8	C1 D15	C2 D1	C3 D1	C4-6 D1	C7 ^b + D1	NA	NA	NA	NA	
Day	-28	1	8	15	22	43	64-106	127+	NA	NA	NA	NA	
Window (days)	NA	0	±2	±2	±7	±7	±7	±7	NA	±7	±7	±7	SECTION:
Survival Status												X ^s	4.3.4
Anti-cancer treatment											X	X ^s	4.3.3, 4.3.4
Subsequent response /progression data												X ^t	5.8

a A cycle is defined as 21-day treatment period.

b Visit schedule changes after Cycle 7 Day 1 from every 21 days (3 weeks) to every 42 days (6 weeks).

c Consent may be taken prior to 28-day window if required.

d Taken following progression on the latest line of therapy.

e The optional second tumour tissue sample can be taken as part of the same procedure as the mandatory screening biopsy for mutation analysis.

f Archival tumour sample only to be submitted after T790M positive status confirmed by central testing. Not required for T790M negative patients.

g To be completed pre-dose.

h If screening assessments have been performed within 14 days prior to starting study treatment they do not have to be repeated on Visit 2 if the patient's condition has not changed.

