7.5 Compliance

The administration of all study drugs should be recorded in the appropriate sections of the Case Report Form.

Patients should return all unused medication and empty containers to the investigator.

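### The 21-day dispensing rule in protocol Section 7.2 was never aligned with the 42-day visit interval that applies after Cycle 7 Day 1

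*Supplement*

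**What the plan says.** Section 7.2 of the protocol of 26 February 2014 gives the quantity: "At each dispensing visit, sufficient AZD9291 for 21 days treatment, plus overage, will be dispensed". It gives no figure for the overage. The next sentence concerns which bottles are handed out: "Individual bottles will be dispensed in accordance with the medication identification numbers provided by the IVRS/IWRS". The same section prescribes one 80 mg tablet a day and adds: "Doses should not be missed".

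Table 1 defines a cycle as 21 days. Its row "Dispense study medication" is marked at Day 1 of Cycles 1, 2, 3, 4 to 6, and 7 onward, and at no other visit. Footnote b, repeated in substance in Section 4.2, reads: "Visit schedule changes after Cycle 7 Day 1 from every 21 days (3 weeks) to every 42 days (6 weeks".

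Section 7.5 says of leftover tablets: "Patients should return all unused medication and empty containers to the investigator". It does not say when.

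Amendment 1 does not touch Section 7.2. Amendment 2 revises only its fasting paragraph. The dispensing sentence therefore stands in the latest version.

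**The concern.** Through Cycle 6 the supply and the visit interval agree: 21 days of drug for a 21-day gap. From Cycle 7 Day 1 the gap doubles and the stated supply does not. A site or supply vendor who applied the sentence literally would dispense half the tablets needed to reach the next visit, apart from an overage of unknown size.

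Continuity of treatment is what is at stake, for patients still on drug beyond day 147. Treatment of that length is planned for: the protocol sets no maximum duration, and Section 8.9.2 reports duration of response beyond 6, 9 and 12 months.

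**Working it through.** This is arithmetic on the visit schedule; no power or precision formula applies.

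**Inputs**
- Supply per dispensing visit: 21 days plus overage *v*, not stated (Section 7.2).
- Dose: one tablet a day (Section 7.2).
- Nominal dispensing days: 1, 22, 43, 64, 85, 106, 127 (Table 1, 21-day cycles).
- Visit interval after Cycle 7 Day 1: 42 days (Section 4.2; Table 1 footnote b).
- Visit window: ±7 days (Table 1), taken here around the nominal day counted from first dose.

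**Step 1: the plan's figure, where it fits.** Successive dispensing days up to day 127 are 21 days apart. Need is 21 tablets, supply is 21, shortfall 0. The rule is right for this part of the schedule.

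**Step 2: after Cycle 7 Day 1, nominal visits, no overage.**
- Cycle 7 Day 1 = 6 × 21 + 1 = day 127.
- Last supplied day = 127 + 20 = day 147.
- Next visit = 127 + 42 = day 169.
- Unsupplied: days 148 to 168 = 21 of 42 days.

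**Step 3: window on the next visit.** By Cycle 7 Day 1 there have been seven dispensings, so 7 × 21 = 147 tablets. Doses due before a visit on day D number D − 1, so the shortfall is D − 1 − 147.

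| Next visit | D | Shortfall | Share of a 21-day supply |
|---|---|---|---|
| −7 days | 162 | 14 days | 67% |
| nominal | 169 | 21 days | 100% |
| +7 days | 176 | 28 days | 133% |

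This count carries tablets forward from one visit to the next.

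**Step 4: overage (assumed range, since none is stated).** Counting only the overage issued at Cycle 7 Day 1, the shortfall is max(0, L − 21 − *v*), where L is 35, 42 or 49 days.

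| *v* (days) | L = 35 | L = 42 | L = 49 |
|---|---|---|---|
| 0 | 14 | 21 | 28 |
| 7 | 7 | 14 | 21 |
| 14 | 0 | 7 | 14 |
| 21 | 0 | 0 | 7 |
| 28 | 0 | 0 | 0 |

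At the nominal interval the overage must equal the supply itself to close the gap.

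**Step 5: what if overage accumulates?** If patients keep it, seven dispensings give 7*v* spare tablets, so *v* = 3 would cover the first 42-day interval (7 × 3 = 21). By the end of the second, the spare is 8 × 3 = 24 against a cumulative need of 2 × 21 = 42, leaving 18 days short. Accumulation postpones the shortfall; it does not make the rule fit the schedule.

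**The case against.** The strongest reply is that supply was meant per cycle. Cycles stay at 21 days, and Table 1 is headed "Treatment Period (further treatment cycles as per Cycle 7", so a six-weekly visit spanning two cycles would naturally hand out two 21-day supplies. The bottles issued also follow the numbers the IVRS/IWRS returns, so that system may settle the quantity. Both are plausible, and both lower the practical risk. Neither removes the conflict. Section 7.2 ties the quantity to the dispensing visit, and nothing in the documents says that two supplies are issued at one visit. The per-cycle rule is reached only by overriding the written one.

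Four stronger readings are tempting and not supported:

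- **That patients will run out of drug.** The overage and the IVRS/IWRS quantities are not given, so the documents do not show this.
- **That PFS or duration of response will be biased.** This needs a small overage, an allocation that ignores the 42-day schedule, and no reaction from site or patient. Section 7.2 also requires dose interruptions to be recorded in the eCRF, so a gap would be visible. No effect on these endpoints can be quantified.
- **That the shortfall ranges from 7 to 35 days.** This comes from applying the window at both visits (intervals of 28 to 56 days) with no tablets carried over. The return instruction in Section 7.5 has no timing and does not establish that usable tablets are taken back at each visit.
- **That a later change left Section 7.2 out of date.** The 21-day sentence and the 42-day interval both stand in the protocol of 26 February 2014. They were never aligned.

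**Conclusion.** The inconsistency is real and minor. Before overage, the written rule leaves 21 of 42 days unsupplied at the nominal interval, and 14 to 28 days across the ±7-day window at the next visit. This assumes one tablet a day, windows set around nominal days from first dose, and tablets carried forward between visits.

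Confidence is high that the texts conflict. Whether any gap would arise in practice cannot be judged from these documents. The reason to act is continuity of treatment. The sample size, the ORR precision and the other statistical figures in the plan do not depend on it.

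**What to change.** Amend the dispensing sentence in Section 7.2 along these lines: *Through Cycle 6 Day 1, each dispensing visit supplies AZD9291 for 21 days plus overage. From Cycle 7 Day 1 onward, each dispensing visit supplies AZD9291 for 42 days (two 21-day supplies) plus overage sufficient to cover the ±7-day visit window.*

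Counted from the nominal day, a next visit at +7 days needs 42 + 7 = 49 days of drug. The exact overage can be left to the sponsor, who knows when unused tablets are taken back. Confirm that the IVRS/IWRS allocates these quantities.

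The cost is one sentence in an amendment, a check of the IVRS/IWRS configuration, and slightly more drug dispensed and returned.
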